Participants will be recruited either during or post-emergency department (ED; including urgent care) visit at Hurley Medical Center (HMC) which is a public, academic, Level-1 Trauma Center located in Flint, Michigan. Enrollment will focus on recruiting approximately 50% males and 50% females. Potential participants will be screened for eligibility using a 5-10 minute screening survey. Randomization to conditions will be balanced based on sex (male, female), age (ages 18-20, ages 21-25), and more than once a day cannabis use, using urn randomization in blocks of 4.

Modifications to recruitment procedures for the purposes of remote recruitment are described here:

For remote recruitment, RAs will contact ED patients ages 18-25 who meet screening inclusion criteria (listed below in "Study Eligibility Criteria") within 60 days of discharge to invite them to consent and complete a web-based screening survey. RAs

Full Study Title: Harnessing social media to reduce cannabis use among adolescents and emerging adults in an urban emergency department

will determine who to contact by viewing HMC's ED medical records (same records viewed as during in-person recruitment), they may send a text message to let the participant know we will be contacting them. Using contact information obtained from the medical record, RAs will follow a phone recruitment script for these procedures, obtain verbal informed consent prior to starting the screening survey and document RA name and date consent is obtained.

After consenting, interested participants may choose to self-administer the survey online or complete an RA-administered version over the phone. For verbally consented participants completing the survey online, a copy of the screening consent form will appear at the beginning of the survey. Other participants may prefer to interact with us via text message, in this case we may adapt the phone script for text messaging, and we will obtain electronic consent at the beginning of the screening survey. Participants recruited remotely will not receive a token gift for completing the screening survey.

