Those meeting eligibility criteria (see below) on the screening survey will be eligible for enrolling in the trial and completing the baseline procedures. RAs will explain the study to participants during the baseline consenting process. Interested participants will be enrolled in the study after completing verbal consent over the phone and RAs will document their name and date consent is obtained. A copy of this consent form will also be shown online at the beginning of the baseline survey.

Briefly, because participants will be identified via reviewing the ED medical chart we are requesting an update to our **waiver of HIPAA authorization** to accommodate remote recruitment. We are also requesting an update to our **waiver of documentation** to accommodate remote recruitment. At screening, consistent with prior procedures, interested participants will be asked to complete an electronic informed consent or verbally consent to complete the screening assessment. In addition, this waiver will apply to remote completion of baseline procedures allowing for verbal consent obtained over phone.

Study Eligibility Criteria

Screening inclusion criteria: (1) Emerging adults (ages 18-25) presenting to the Emergency Department (including Urgent Care) on the day of in-person recruitment; presenting within 60 days of contact for remote recruitment and (2) owning a working smartphone. Additional baseline inclusion criteria: (3) weekly or more frequent non-medical cannabis use for the past 3 months; and (4) any Snapchat use in the past month. Exclusion criteria: (1) Does not understand English; (2) presenting to the ED for sexual assault or acute suicidality; (3) unable to provide informed consent due to medical/psychiatric reasons/having a legal guardian; (4) Aim 1 participant.

Study Procedures

After enrolling in the study, EAs will complete a 15-20 minute baseline survey, a 15-30 minute RA administered semi-structured Timeline Follow-Back calendar (TLFB), and a urine drug screen (UDS) (for in-person recruitment), before they are randomized to condition (*SnapCoach* or EUC). They will also complete a 3-minute immediate post-test and provide contact information. For these activities participants will receive \$40. When a participant is recruited

Full Study Title: Harnessing social media to reduce cannabis use among adolescents and emerging adults in an urban emergency department

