Demographics: Age, Sex, Race, Ethnicity (adapted from national surveys, e.g., the Youth Risk Behavior Survey ³⁹)	S
Demographics: Gender identity, Sexual Orientation, School Status, Employment, Living Situation, Children, Marital Status, Pregnancy (adapted from national surveys, e.g., the Youth Risk Behavior Survey ³⁹)	B,3M
Demographic: Parents and Personal Income ^{86,87}	B
Service Utilization: ER and Urgent Care ^{86,87}	B,3M
1-minute delay discounting task ⁸⁴	S,1M,3M
Snapchat involvement (modified) ^{22,40,41,42}	S
Comprehensive Marijuana Motives (modified) ⁴³	B,3M
Perceived risk of cannabis (modified for different cannabis modalities) ⁴⁴	S,1M,3M
Importance, Self-Efficacy, Intention Rulers ^{45,46}	B,I,1M,3M
Cannabis acquisition, strain, and medical marijuana ^{47,48,49,50,51,74}	
Cannabis acquisition	B,1M,3M
Preferred Marijuana Strain	B
Medical Marijuana	S,3M
NIDA modified ASSIST ^{65,66,85}	S,3M
Alcohol use frequency (AUDIT-C) ⁷³	S,3M
Tobacco and Nicotine use (modified) ⁶⁵	S,1M,3M
Mental health: Patient Health Questionnaire-2; Generalized Anxiety Disorder-2 ^{52,53,54,55,56,57,58,59,60,61}	B,1M,3M
Protective Behavioral Strategies for Marijuana (modified) ⁷⁷	B,3M
Gun Carriage ^{75,76}	B
Hope ⁷⁸	B,1M,3M

Peer/Social Influences
	
Cannabis online norms and exposure ^{64,41}	B,1M,3M

Exploratory Outcomes
	

Full Study Title: Harnessing social media to reduce cannabis use among adolescents and emerging adults in an urban emergency department

Cannabis use method, frequency and quantity ⁷⁴ (modified) Smoke, Vape, and Dab (frequency, quantity) Drink and all methods combined (frequency, quantity) Number of days all methods combined Number of days vaped	S,3M B,3M B,1M,3M 1M
Cannabis and Other Drug Use Frequency, Alcohol Quantity/Frequency(TLFB) ^{67,68,69,70}	B,3M
Brief Marijuana Adolescent Consequences Questionnaire (modified) ⁷¹	B,3M
Impaired driving (modified) ⁷²	B,3M
Primary Outcomes: Feasibility/Acceptability of Intervention	
Brief Intervention acceptability ratings (created for this study)	I
Snapchat acceptability ratings (created for this study)	1M
Brief intervention feasibility (e.g., % of participants completing brief intervention)	I
Snapchat health coaching feasibility (e.g., % of participants who complete process of adding health coach on Snapchat, % of participants who reply to at least 1 Snapchat message)	I,1M

Data Management and Analysis

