Randomized participants will be included in intent-to-treat analyses, regardless of group engagement. By design, groups will be balanced based on sex, age, and more than once a day cannabis use, using urn randomization in blocks of 4; we will validate randomization by evaluating covariate balance between groups. If significant differences that could be confounding emerge, we will adjust for those variables or conduct stratified analyses.

Analyses pertaining to primary outcomes of feasibility and acceptability of the intervention are primarily descriptive in nature (e.g., % completing the assigned intervention condition, % engaging in Snapchat messaging, ratings of intervention satisfaction).

For analyses of other exploratory outcomes pertaining to cannabis use, alcohol, and drug use, we will first compare groups on cannabis quantity and frequency using basic two sample comparisons, operating on the pre-post differences (e.g., 3M-Baseline) to test for treatment effects. Our first choice will be a two-sample *t*-test to compare the pre-post differences between groups; considering non-parametric alternatives as needed. To assess changes in the dependent measures (e.g., use days, quantity, cannabis consequences) over follow-up we will use generalized linear mixed models (GLMMs) to jointly study the 1M and 3M outcomes, where possible, while adjusting for correlations between data points (e.g. repeated measurements on individuals). While adjustment for the baseline measurement is important for guarding against regression to the mean in RCTs¹⁹⁵, using this baseline adjustment at every time point can result

Full Study Title: Harnessing social media to reduce cannabis use among adolescents and emerging adults in an urban emergency department

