in overestimation of the treatment effect when there are multiple follow-up points. It has been shown that baseline adjustment at only the first follow-up (1M in this case) corrects this overestimation while also guarding against regression to the mean, which will be our approach. Within this framework, we will conduct exploratory sub-analyses of whether the intervention effect is accumulating or weakening over time, by including time-by-group interactions. If the need is ascertained, we will control for confounders through their inclusion in the model as covariates. Our initial specification will be a linear mixed effects model (with Gaussian error distribution) with only a random intercept to capture within-individual dependence, but this choice will be scrutinized by examining model diagnostics and evaluating the veracity of modeling assumptions. As the need is ascertained, we will examine other distributional choices (e.g., Poisson, Negative Binomial) and more complex random effects structures (e.g., autoregressive).

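### Cannabis measures followed up only at 3 months are first compared by an unadjusted change-score t-test, which is less precise than baseline adjustment when the baseline slope is below 1

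*Combined protocol and SAP*

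**What the plan says.** Data Management and Analysis sets out two stages for the exploratory substance use outcomes.

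- **First stage.** Cannabis quantity and frequency are compared by a two-sample t-test "operating on the pre-post differences (e.g., 3M-Baseline) to test for treatment effects", "considering non-parametric alternatives as needed". No covariate is included. Other variables are adjusted for only if a significant imbalance appears.
- **Second stage.** Mixed models are used "to jointly study the 1M and 3M outcomes, where possible". Here the plan gives its reason for adjusting: "While adjustment for the baseline measurement is important for guarding against regression to the mean". It then limits the adjustment to one visit, because "baseline adjustment at only the first follow-up (1M in this case) corrects this overestimation".

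Table 1 gives the visit schedule. The row "Cannabis and Other Drug Use Frequency, Alcohol Quantity/Frequency(TLFB") is collected at baseline and 3M only. In the row for method, frequency and quantity, matching the timing codes to the items in order gives:

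- smoke, vape and dab: screening and 3M
- drink and all methods combined: baseline and 3M
- number of days, all methods: baseline, 1M and 3M
- days vaped: 1M

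Only the all-methods day count is listed before randomisation, at 1M and at 3M.

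Under Recruitment Procedures, "Randomization to conditions will be balanced based on sex (male, female), age (ages 18-20, ages 21-25), and more than once a day cannabis use". The power section intends to take effect-size estimates and confidence intervals from the pilot and to use its data in planning the next trial. It does not say which model supplies them.

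**The concern.** A change score fixes the slope of the 3M value on baseline at 1. ANCOVA estimates that slope, so it is more precise whenever the slope is clearly different from 1. The plan's stated reason for adjusting is regression to the mean, which implies a slope below 1 unless the SD grows enough by 3M to offset it. The first comparison therefore does not follow the plan's own reasoning.

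The mixed model does not clearly fill the gap, because its baseline adjustment is attached to a visit that most of these measures lack.

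What is at stake is precision, not bias or false positives. If the first comparison supplies the pilot effect sizes, their intervals will be wider than the data allow. The power section itself concedes that pilot effect sizes can be imprecise.

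**Working it through.** **Inputs.** From the documents: 50 per arm and d = 0.56 at more than 80% power (power section); blocks of 4 with three balancing factors (Recruitment Procedures); visit timing (Table 1). Assumed: two-sided alpha 0.05, correlation r between baseline and 3M, and SD ratio k = SD(3M)/SD(baseline).

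**1. The plan's figure.** d × √(n/2) = 0.56 × √25 = 2.80, and Φ(2.80 − 1.96) = Φ(0.84) = 0.80. The noncentral t gives 79.2%. The figure reproduces, but for a comparison of means at one time point, not of change scores.

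**2. Variances**, in units of the baseline variance, with slope b = rk:

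- Change score: 1 + k² − 2rk
- ANCOVA residual: k²(1 − r²)
- Difference: (1 − rk)² = (1 − b)²

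The difference is never negative and is zero only at b = 1. With equal SDs the ratio ANCOVA/change is (1 − r²)/(2(1 − r)) = (1 + r)/2.

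| r (k = 1) | Change | ANCOVA | Ratio | CI excess, √(1/ratio) − 1 |
|---|---|---|---|---|
| 0.3 | 1.40 | 0.91 | 0.65 | 24% |
| 0.5 | 1.00 | 0.75 | 0.75 | 15% |
| 0.7 | 0.60 | 0.51 | 0.85 | 8% |
| 0.8 | 0.40 | 0.36 | 0.90 | 5% |

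Estimating the slope inflates the ANCOVA variance by about 1 + 1/(100 − 4) = 1.010. With equal SDs this cancels the gain only when the slope is within about 0.02 of 1.

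**3. Power** for a difference of 0.56 single-time-point SDs (normal approximation, k = 1), change score against ANCOVA: 65.8% against 83.5% at r = 0.3; 80.0% against 89.9% at r = 0.5; 95.1% against 97.5% at r = 0.7.

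**4. CI width under the stratified design.** Simulation under the null: N = 100, normal data, permuted blocks of 4 in 8 strata, and the top 40% of baseline flagged as high use. ANCOVA includes baseline and the three factors. Excess width of the change-score 95% CI:

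| Assumption | r = 0.3 | 0.5 | 0.7 | 0.8 |
|---|---|---|---|---|
| Equal SDs | 23% | 15% | 8% | 5% |
| k = 0.8 | 40% | 31% | 25% | 24% |
| k = 1.25 | 12% | 5% | 0% | −1% |
| Equal SDs, 20% attrition | 23% | 14% | 7% | 4% |
| Lower 25% of baseline removed* | 13% | 8% | 4% | 2% |
| Lower 50% of baseline removed* | 9% | 5% | 2% | 1% |

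*r is the correlation before selection. These rows represent the entry rule, "weekly or more frequent non-medical cannabis use for the past 3 months". Selecting on baseline narrows its SD but leaves the slope unchanged: at r = 0.5 with the lower quarter removed, the in-trial correlation is 0.39 and k is 1.29, so b = 0.39 × 1.29 ≈ 0.50.

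At equal SDs and r = 0.5 the mean half-widths are 0.396 (change), 0.344 (ANCOVA, baseline only) and 0.346 (with factors). Nearly all the gain comes from the baseline value.

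**5. Actual and reported precision.** Balancing on a high-use flag cut from the measure itself already removes part of the chance baseline imbalance, which the t-test's standard error ignores. At equal SDs and r = 0.3 / 0.5 / 0.7 / 0.8:

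- Flag cut from the measure: true sampling-variance ratio (change/ANCOVA) 1.18 / 1.12 / 1.07 / 1.03, so true standard errors differ by 9 / 6 / 3 / 1.5%. The rest of the CI excess is an oversized standard error, and the t-test rejects in only 2.6 / 3.4 / 4.2 / 4.3% of null trials.
- Flag unrelated to the measure: variance ratio 1.52 / 1.32 / 1.19 / 1.09, test size about 5%, and the same CI excess.

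ANCOVA size stays at 4.4–5.5%, and bias is at most 0.006 in every cell of the main grid.

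**The case against.** The strongest reply is that the plan already adjusts. The t-test is only a first look. The mixed model lists quantity and consequences among its outcomes, and these have no 1M value. Its rule is to adjust at the first follow-up, which for such measures is 3M; the model then reduces to ANCOVA. This reading is reasonable, but the text names 1M and does not state it. It would also leave the first comparison unadjusted and the source of the effect sizes open.

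Second, the CI figures can overstate the real loss. If the high-use flag is cut from the measure, the true standard errors differ by 9% or less at equal SDs. With the lower quarter of baseline also removed, the variance ratio is about 1.07 at most, or roughly 3% in standard error. This stands for that case. With an unrelated flag, the sampling-variance ratios show a true loss about as large as the CI figures. In both cases the reported interval, which the next trial's planners would read, is too wide.

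Third, the correlations and SDs are assumed, the data are simulated as normal, and permuted blocks stand in for the plan's urn procedure. Regression to the mean does not guarantee a slope below 1 if the SD grows: k = 1.25 with r = 0.8 gives a slope of exactly 1 and no gain. This also stands, and it is why a range is shown.

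Fourth, the outcomes are exploratory. That limits the importance of the point but does not remove it.

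**Conclusion.** The concern holds. For cannabis quantity and frequency measures with 3M as their only follow-up, the first comparison gives up precision that a pre-randomisation value already in hand would supply, unless the slope is close to 1. With equal SDs the 95% CI is 5–23% wider over r = 0.8 to 0.3. It is 1–13% wider if eligibility truncates baseline use, and there is no loss at a slope of 1. These figures rest on assumed correlations, SD ratios and normal data.

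The change-score test remains unbiased and does not inflate false positives. The descriptive primary outcomes are untouched. Whether the mixed model was meant to cover these measures cannot be settled from the text. The assignment of timing codes within the method, frequency and quantity row relies on their order in a broken table; the Timeline Follow-Back row does not.

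**What to change.** In Data Management and Analysis, for each cannabis quantity or frequency measure with 3M as its only follow-up:

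- Make the first comparison a linear regression of the 3M value on arm, the pre-randomisation value of the same measure (screening or baseline, as scheduled in Table 1), sex, age group and use more than once a day.
- Report the adjusted mean difference with its 95% CI, using a robust variance if the data are skewed.
- Keep the change-score t-test as a supplementary analysis.

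In the power section, name this model as the source of the pilot effect sizes for these measures. If the mixed model was meant to adjust them for baseline at 3M, say so where the 1M rule is given.

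The cost is one or two sentences. All the covariates are already collected. The four extra degrees of freedom cost about 0.5–1% in CI width when the slope is near 1. The baseline value supplies the precision. The three factors change CI width by only about 0.5% and are included so that the analysis matches the randomisation.

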Other analyses. *Moderation:* To assess potential moderators we will include interactions with treatment group in the GLMM models above. Potential effect modifiers will include sex and age. *Mediation:* To test if cannabis motives and other variables (e.g., mental health symptoms) mediate treatment effects, we will use Imai's causal mediation analysis framework, that is robustly implemented in the R package *mediation*. Traditional mediation analysis can be susceptible to bias; one source of this bias is the limitation to the classes of statistical models (e.g. the linear structural model of Baron and Kenny), that can be accommodated in traditional mediation analysis. Under technical assumptions of sequential ignorability, mediation effects are identifiable using Imai's framework when models for the mediator and for the outcome that are non-linear, have discrete (nominal or ordinal) or continuous outcomes, include random effects, or are non-parametric. *Engagement:* Daily content ratings assessed by tallies from Snapchat messages logs (e.g., content, messages sent/received) will be calculated for different content areas (e.g., free time, stress, drug/alcohol-related) and assessed descriptively to see types of content with high response rates. *Cost:* To estimate intervention we will calculate summary statistics for the total intervention-specific costs and mean costs per participant, with confidence intervals. Costs will be reported with/without start-up and development, for example, including costs for recruiting and training coaches as well as their clinical supervision. As with prior work, net costs (savings) will be calculated by subtracting mean costs per participant in the control group from costs per participant for the assigned condition, also calculating the incremental cost effectiveness ratio (difference in mean cost of intervention vs. control divided by difference in mean effectiveness between intervention and control). Change in health benefits will be measured as the difference in cannabis consequences per month for the intervention vs. the control, expressed in dollars per consequence averted. Sensitivity analyses to evaluate alternate assumptions for estimated costs will be conducted. Given likely skewness, we will identify appropriate methods for generating confidence intervals that do not rely on the normal distribution (e.g., non-parametric bootstrapping).

Power calculation and sample size

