Aim 2: The sample size is $N = 100$ (approximately 50 per group). For our primary analytic goal – examining feasibility and acceptability this is acceptable. With regard to other exploratory analyses estimating treatment effects – we are comparing two groups of size $n = 50$. Assuming no substantial covariate adjustment is needed, testing the significance of the treatment effect at a single time point will be equivalent to the comparison of two means, for which we use Cohen's D (0.2: small, 0.5: medium, 0.8: large) as an effect size. Under the expected sample size, we will have sufficient power ($>80\%$) to detect effects on both our cannabis and other substance use outcomes if $d > 0.56$, a medium effect size. Although the required effect size is non-negligible, the proposed pilot will provide the critical data necessary to inform the power analyses for a subsequent efficacy trial. While effect sizes from pilot studies

Full Study Title: Harnessing social media to reduce cannabis use among adolescents and emerging adults in an urban emergency department

can have large standard errors and be unstable,²⁰² we can use these pilot data to estimate point estimates and confidence intervals for our treatment effect sizes using the R package MBESS²⁰³.

Data Confidentiality Plans

Our study team will take the following steps to minimize potential confidentiality breaches. As done in prior research and deemed HIPAA compliant by the IRBs at University of Michigan (UM) and HMC by use of a waiver of HIPAA authorization, minimal clinical data will be collected on ED patients who refuse to participate in the screening survey, and on ED patients who the research assistants fail to approach or contact (for remote recruitment). ED-based intervention, TLFB assessment sessions and any phone interviews (e.g., in the event a person cannot attend a follow-up in person, or during remote recruitment, we can administer the TLFB by phone) will be audio-recorded and will be destroyed after the conclusion of the study.

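### Adjusting the mixed model for baseline at 1 month only rests on a reason that fails under randomisation, and leaves its 3-month contrast unadjusted and less precise

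*Combined protocol and SAP*

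**What the plan says.** The Data Management and Analysis section gives two exploratory efficacy analyses. The first is a two-sample t-test, "operating on the pre-post differences (e.g., 3M-Baseline) to test for treatment effects". The second is a mixed model to "jointly study the 1M and 3M outcomes, where possible".

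For the mixed model, the plan accepts that baseline adjustment guards against regression to the mean, but says that applying it at every visit can result "in overestimation of the treatment effect when there are multiple follow-up points". It then says that "baseline adjustment at only the first follow-up (1M in this case) corrects this overestimation while also guarding against regression to the mean", and adopts this as its approach. No baseline term, and no lagged 1-month term, is described for 3 months. The initial model is Gaussian with "only a random intercept to capture within-individual dependence"; time-by-group terms are added in exploratory sub-analyses.

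In Table 1, the only cannabis-use outcome recorded at baseline, 1 month and 3 months is "Number of days all methods combined". The Timeline Follow-Back and the consequences questionnaire have no 1-month measurement. For moderators, the Other analyses paragraph says "we will include interactions with treatment group in the GLMM models above". The Power calculation section says the pilot will "inform the power analyses for a subsequent efficacy trial".

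**The concern.** The stated reason does not apply to this design. Arms are randomised, so baseline has the same expected value in both, and a linear baseline covariate at each visit cannot shift the group contrast on average.

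The rule also removes the protection the plan wants at the time point it cares about most: the Objective section places the cannabis outcomes at 3 months. Without baseline in the 3-month part of the model, chance imbalance passes into the estimate and variance that baseline would explain goes back into the error. Moderator analyses built on the same models inherit the rule. Because the pilot is meant to supply effect sizes and intervals for a later trial, a wider and imbalance-sensitive estimate is a real cost.

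**Working it through.** **Inputs.** 50 per arm and detectable d above 0.56 at more than 80% power, assuming no substantial covariate adjustment (Power calculation section). Alpha is not stated there; 0.05 two-sided is assumed. The documents give no correlation between baseline and 3 months (ρ), so 0.3, 0.5 and 0.7 are assumed. Outcome SD is set to 1 at every visit, with complete data.

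**The plan's own figure.** Normal approximation: (1.960 + 0.842) × √(2/50) = 0.560. The noncentral t gives 0.566, and 79.2% power at d = 0.56. The stated figure reproduces.

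**Does adjusting at both visits overestimate?** Simulated trials with a true effect of -0.40 at both visits (2,000 replicates for each of three correlation sets) gave mean estimates from -0.404 to -0.398. A separate simulation with a true 3-month effect of 0.30 gave 0.292 to 0.300. There is no overestimation.

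**What does the 1-month-only rule estimate at 3 months?** With group-by-visit terms, the 3-month regressors (intercept, group) are a subset of the 1-month regressors (intercept, group, baseline). With complete data, generalised least squares for the smaller equation reduces to ordinary least squares, so the 3-month contrast is the raw difference in means, under a random intercept or an unstructured covariance. In simulation the two differed by less than 1.2 × 10⁻¹⁴.

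**Size at 3 months.** Adjustment multiplies the variance by 1 - ρ². Hence the SE ratio is 1/√(1 - ρ²), the equivalent loss is 100ρ² participants, and the detectable d with adjustment is 0.566 × √(1 - ρ²). One SE of the baseline difference under simple randomisation is √(2/50) = 0.2 SD, and it shifts the unadjusted contrast by 0.2ρ. Balancing on more-than-daily use should make such an imbalance less likely.

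| ρ | SE, unadjusted ÷ adjusted | Equivalent loss of 100 | Detectable d, unadjusted → adjusted | Shift from 0.2 SD imbalance |
|---|---|---|---|---|
| 0.3 | 1.05 | 9 | 0.57 → 0.54 | 0.06 SD |
| 0.5 | 1.15 | 25 | 0.57 → 0.49 | 0.10 SD |
| 0.7 | 1.40 | 49 | 0.57 → 0.40 | 0.14 SD |

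Simulated SDs of the 3-month contrast agree (4,000 replicates; 1-month-only against both visits): 0.197 against 0.190, 0.201 against 0.174, and 0.199 against 0.141.

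**The 1-month contrast.** It is only partly protected. Write r₁ for the baseline to 1-month correlation and r₁₃ for the 1-month to 3-month correlation. Fitting the visits jointly with an unstructured covariance gives a 1-month baseline coefficient of (r₁ - ρr₁₃)/(1 - ρ²) instead of r₁. For (r₁, ρ, r₁₃) = (0.6, 0.5, 0.7) this is (0.6 - 0.35)/0.75 = 0.33, so 0.6 - 0.33 = 0.27 of the imbalance remains. Simulation gave 0.27 for that set, and 0.12 and 0.39 for (0.4, 0.3, 0.5) and (0.7, 0.7, 0.8). Under a random intercept the three values were 0.33, 0.13 and 0.51. With baseline at both visits the remainder is about 0.

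**The pooled group effect (no time-by-group term).** For the same three sets, in order of ρ, the SDs were 0.163 against 0.158, 0.172 against 0.149, and 0.177 against 0.127: 3%, 15% and 40% larger under the rule. It carried 0.20, 0.43 and 0.62 of the imbalance. Type I error was near nominal (4.7% to 5.5% over the five correlation sets run).

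**Secondary point.** Under the initial random-intercept model, the model SE at 3 months was 2% to 10% too small over those five sets (type I error 5.6% to 7.5%). Much of this comes from the equal-variance random intercept, since type I error was 4.6% to 7.3% with baseline at both visits. With an unstructured covariance the rule gave 4.8% to 5.4%.

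**The case against.** The best case against is one of scale. Efficacy is exploratory, a separate 3-month contrast appears only when time-by-group terms are added, and one cannabis-use outcome is affected. The first-choice test at 3 months, the change score, already uses baseline. Its SE relative to the adjusted analysis is √(2/(1 + ρ)): 1.24, 1.15 and 1.08 at ρ = 0.3, 0.5 and 0.7. Taking the better of the two planned 3-month estimates, the loss is therefore about 5%, 15% and 8%. The plan also allows adjustment if significant, potentially confounding imbalance appears, and treats the random intercept as a starting choice subject to diagnostics. Use days are bounded, so Gaussian results are approximate. Finally, if the authors meant 3 months to be adjusted for the 1-month value, the raw-difference result would not apply.

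Much of this limits the point, and the 49-participant figure describes the mixed model only. It does not rescue the rule. The pooled effect, which is the model's base form, loses precision too. The imbalance clause would not catch a 0.2 SD difference and would not restore precision. A lagged 1-month adjustment is nowhere stated. A sound t-test beside the model does not justify a weaker specification within it, and the plan does not say which estimate will feed the later trial.

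**Conclusion.** The concern holds and should be fixed. The overestimation rationale is wrong for a randomised comparison, and the rule leaves the 3-month contrast with no baseline adjustment. The cost is precision and sensitivity to chance imbalance, not bias on average: a 3-month SE 5% to 40% larger for ρ from 0.3 to 0.7, assuming equal SDs, Gaussian outcomes and no dropout. It is forgone efficiency, not a shortfall against the stated d > 0.56, which already assumes no substantial covariate adjustment. The scope is exploratory outcomes measured at both 1 and 3 months (among cannabis-use measures, use days) and the moderator models built on them. The primary outcomes are unaffected. No fault is claimed in the time-by-group test, whose type I error stayed at 5.2% to 5.8%.

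**What to change.** Delete the 1-month-only rule and its overestimation rationale. For outcomes measured at baseline, 1 month and 3 months, specify group, visit, group-by-visit, baseline and baseline-by-visit, so that baseline enters at both follow-ups. Use an unstructured 2×2 covariance, or at least visit-specific variances, and report the 3-month contrast from that model. For outcomes measured only at baseline and 3 months (Timeline Follow-Back frequency, consequences), state that the model is ANCOVA at 3 months; the present text does not say how baseline enters for them.

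The cost is two or three sentences and one more model term. No new data are needed.
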